9.1 Subject Disposition

The subject will be categorized for each cohort.

1) Cohort 1

Subjects with informed consent, subjects discontinued before administration of DSP-5423P (tablet), subjects took DSP-5423 (tablet) in DSP-5423 (tablet) treatment period, subjects who didn't apply DSP-5423P after completion of DSP-5423 (tablet), subjects who applied DSP-5423P in DSP-5423P application period, subjects who completed DSP-5423P application period, and subject who early terminated from DSP-5423P application period.

2) Cohort 2

Subjects with informed consent, subjects discontinued before application of DSP-5423P, subjects took DSP-5423P in DSP-5423P application period, subjects who completed DSP-5423P application period, and subject who early terminated from DSP-5423P application period.

List of the study disposition, list of subject who discontinued the treatment of DSP-5423 (tablet) treatment period, and list of subject who discontinued the treatment of DSP-5423P application period.

9.2 Analysis Population

The number and percentage of subjects who are included in each analysis population or treated with DSP-5423P will be summarized for each cohort and cohort total. The list of analysis population and subjects who excluded from each population will be presented.

9.3 Important Protocol Deviations

IPDs will be discussed and determined at a blind data review meeting before DBL. Potential IPDs will be identified through data review by programmatically and manually and review for the deviation log. Subjects with potential IPDs can be, but not limited to:

- Subject who deviated inclusion/exclusion criteria
- Subject who took prohibited concomitant medication/therapy

The number of IPDs, and the number and percentage of subjects with IPD will be summarized by cohort and IPDs defined in Table 5. For Cohort1, IPDs in DSP-5423(tablet) treatment period and ones in DSP-5423P application period will be summarized separately. If a subject has same IPD multiple times, the subject will be counted only one times as such IPD. IPDs will be listed.

Table 5 Important Protocol Deviation Terminology

Categorized important protocol deviation
Deviation from the GCP
Deviation from the eligibility criteria
Use any prohibited medication or therapy
Others

9.4 Demographics and Other Baseline Characteristics

Demographic and baseline characteristics will be summarized based on each analysis population for each cohort and cohort total. They will be also listed. Baseline weight and BMI for Cohort 1 should be the one of DSP-5423(tablet) treatment period.

Sex: Female, Male

Age (years): summary statistics

Age by category: < 65; \geq 65

Race: American Indian or Alaska Native; Asian; Black or African American;
Native Hawaiian or Other Pacific Islander; White; Other

Ethnicity: Hispanic or Latino; Not Hispanic or Latino

Height (cm): summary statistics

Weight (kg): summary statistics

BMI (kg/m^2): summary statistics

Any concomitant disease: No; Yes

Inpatient at informed consent: Inpatient; Outpatient

9.5 Psychiatric History

The summary statistic and the number and percentages will be summarized based on each analysis population for each cohort and cohort total. They will be also listed. Baseline PANSS, CGI-S and DIEPSS for Cohort 1 should be the one of DSP-5423(tablet) treatment period.

Number of episodes of schizophrenia: summary statistics

Number of episodes of schizophrenia: 1; 2; 3; 4; 5 or more, Unknown

Age at initial onset of schizophrenia (years): summary statistics

Age at initial onset of schizophrenia (years):

19 or less; 20 to 29; 30 to 39; 40 to 49; 50 or more

Duration of illness (years)*: summary statistics

Duration of illness (years)*:

< 1; \geq 1 to < 5; \geq 5 to < 10; \geq 10 to < 20; \geq 20 to < 30; \geq 30, Unknown

Duration of current episode (months): summary statistics

PANSS composite subscale at baseline: Positive subscale score > Negative subscale score;
Positive subscale score = Negative subscale score;
Positive subscale score < Negative subscale score

Baseline PANSS total score: summary statistics

Baseline PANSS total score: 59 or less, 60 to 79, 80 or above

Baseline CGI-S score: summary statistics and frequency

Baseline DIEPSS total score (excluding overall severity): summary statistics

* at informed consent, 1 year = 365.25 days

9.6 Medical History

Medical history will be coded using the Medical Dictionary for Regulatory Activities (MedDRA) [Version 19.1], and number and percentage of subjects with any medical history by system organ class (SOC) and preferred term (PT), as well as ones of subjects with any concomitant disease, will be summarized for each cohort and cohort total. All medical history will be listed.

9.7 Prior and Concomitant Medications

For Cohort 1, prior medications are defined as those taken prior to initial dose of DSP-5423 (tablet). For Cohort 2, prior medications are defined as those taken prior to initial application of DSP-5423P. Prior medications will include medications that had been used before participation of the study, which are collected as “Started prior to study” on the CRF.

For Cohort 1, concomitant medications during DSP-5423 (tablet) treatment period are defined as those taken from the initial dose date of DSP-5423 (tablet) through the last dose date of DSP-5423 (tablet). For both Cohort 1 and Cohort 2, concomitant medications during DSP-5423P application period are defined as those taken from the initial application date of DSP-5423P through the last application date of DSP-5423P. Note that the concomitant and prior medications are not mutually exclusive, ie, a medication can be classified as both prior and concomitant medication.

Prior and concomitant medications will be coded using the WHO Drug Dictionary [March 1, 2014 version], Anatomical Therapeutic Chemical (ATC) Classification codes and preferred term (PT, Standardized Medication Name), and summarized for each cohort and cohort total. The number and percentage of subjects who took prior or concomitant medications will be summarized as well.

Prior and concomitant medications will be summarized as the number and percentage of subjects by ATC level and PT for each cohort. If a subjects took same medications in terms of ATC level or PT multiple times, the subject will be counted one time into associated ATC level or PT. In addition, Prior and concomitant medications will be summarized as to following categories defined on the CRF;

Antipsychotics

Antiparkinson drugs

Psychotropic drugs

Hypnotic drugs

The number and percentage of subjects with concomitant use of antiparkinson drugs will be summarized by cohorts and visits. Denominator for visit base summary will be subjects who received DSP-5423 (tablet) during relevant periods or subjects who received DSP-5423P during relevant periods. Note that denominator at Day -1 and one for overall period will be all subjects in Safety Analysis Population. Subgroup analysis for subjects who didn't use antiparkinson drugs at Day -1 will be repeated in the same fashion.

DSP-5423 (tablet) treatment period: (overall)

DSP-5423P application period: Day -1, Week 1 to 2, 3 to 4, 5 to 6, 7 to 12, 13 to 24, 25 to 36, 37 or later, overall (Week 1=Day 1 to 7, Week 2=Day 8 to 14)

Prior or concomitant medications will be listed respectively.

9.8 Treatment Compliance

The percentage of treatment compliance will be calculated for DSP-5423 (tablet) or DSP-5423P according to derivation in section 8.2. Treatment Compliant is defined as a subject with 80% to 120% compliance in condition with no rounding for treatment compliance. Other subjects and also subjects with missing treatment compliance will be seen as non-compliant to study treatment. Summary statistics of treatment compliance will be calculated by visits for each cohort and cohort total as well as the number and percentage of subjects who dropped into the following categories. Treatment compliance will be listed with rounding to one decimal point.

Treatment Compliance: <80%; 80% to 120%; >120%

9.9 Duration of Exposure

Duration of exposure will be calculated following section 8.2. Summary statistics will be calculated by visits for each cohort and cohort total as well as the number and percentage of subjects who dropped into the following categories. Duration of exposure will be listed.

Duration of Exposure (days):

DSP-5423 (tablet) treatment period: 1 to 7; 8 to 14; 15 to 28; 29 to 43; 44 or more

DSP-5423P application period:

1 to 42; 43 to 84; 85 to 168; 169 to 252; 253 to 336; 337 or more

9.10 Daily dose and Cumulative dose

Each kind of daily dose will be calculated following section 8.2. Mean daily dose (mg/day), Maximum daily dose (mg/day) and Modal daily dose (mg/day) will be derived as specified in section

8.2. Those summary statistics will be calculated by visits for each cohort and cohort total, and also the number and percentage of subjects with each dose will be summarized. Those daily doses will be listed.

Cumulative dose will be calculated as specified in section 8.2 and its summary statistics will be calculated by visits for each cohort and cohort total. Cumulative dose will be listed.

9.11 Efficacy Analysis

The efficacy analysis will be performed for each cohort based on safety analysis population.

9.11.1 PANSS Total Score

Observed PANSS total score and change from baseline of DSP-5423P application period will be summarized by visits (including LOCF endpoint) for each cohort. The overtime change of mean of the change from baseline of DSP-5423P application period will be plotted for each cohort with +/-SD.

For DSP-5423(tablet) treatment period in Cohort 1, observed PANSS total score and change from baseline of DSP-5423(tablet) treatment period will be summarized by visits. For both DSP-5423(tablet) and DSP-5423P periods in Cohort 1, the overtime change of mean of the change from baseline of DSP-5423(tablet) treatment period will be plotted with +/-SD.

PANSS score will be listed.

9.11.2 PANSS subscale scores and PANSS five-factor model scores

PANSS subscale scores and PANSS five-factor model scores will be summarized in same fashion as PANSS total score, and listed.

9.11.3 Clinical Global Impression - Severity of Illness (CGI-S)

Observed CGI-S score and change from baseline of DSP-5423P application period will be summarized by visits (including LOCF endpoint) for each cohort. The overtime change of mean of the change from baseline of DSP-5423P application period will be plotted for each cohort with +/-SD.

For DSP-5423(tablet) treatment period in Cohort 1, observed CGI-S score and change from baseline of DSP-5423(tablet) treatment period will be summarized by visits. For entire period in Cohort 1, the overtime change of mean of the change from baseline of DSP-5423(tablet) treatment period will be plotted with +/-SD.

CGI-S score will be listed.

9.11.4 Time to Treatment Discontinuation

All cause discontinuation of DSP-5423P is considered as an event and completion of DSP-5423P

application is considered as a censor, and Kaplan-Meier estimate for 50 percentiles and its 95% CI for time to event will be analyzed. Also the number and percentage of subjects who applied DSP-5423P for 28 weeks or 52 weeks will be summarized. Those analyses will be performed for each cohort overall and also by use of prior antipsychotics (Blonanserin and Other/None).

The final application date of DSP-5423P can be either event date or date of censored. Kaplan-Meier plots for each cohort will be provided. One for each cohort by use of prior antipsychotics will also be provided. Time to Treatment Discontinuation will be listed.

9.11.5 Subgroup analysis for efficacy

For each subgroup, observed PANSS total score and change from baseline of DSP-5423P application period will be summarized by visits (including LOCF endpoint) for each cohort.

Subgroups include Sex, Age (years), use of Prior antipsychotics, Hospitalization status at Screening, Duration of illness (years), and Baseline PANSS total score specified as following. A subject with missing value will not be included in appropriate summary and then ‘missing’ category is not expected to be presented in the tables.

Sex: Male, Female

Age (years): < 65, ≥ 65

Prior antipsychotics: No, Yes

Duration of illness (years): < 5, ≥ 5 to < 10, ≥ 10 to < 20, ≥ 20 , Unknown

Hospitalization status at Screening: Inpatient, Outpatient

Baseline PANSS total score: 59 or less, 60 to 79, 80 or above

9.12 Safety Analysis

Safety analysis will be performed for each cohort and cohort total based on safety population, besides C-SSRS summaries only for each cohort.

9.12.1 Adverse event

The adverse event will be coded using the Medical Dictionary for Regulatory Activities (MedDRA), Version 19.1. Treatment-emergent adverse event (TEAE) is defined as adverse events with start date on or after Day 1. Regardless of cohort, adverse events occurred on same date as the initial date of application of DSP-5423P will be defined as TEAE. All adverse events, regardless of TEAE or not, will be listed. A treatment-related TEAE is defined as a TEAE for which the causal relationship to the study treatment is either ‘definite’, ‘probable’, or ‘possible’.

The summary of TEAE will include the number of event, and the number and percentage of subjects which are classified in the following TEAE or treatment-related TEAE categories. Extrapyramidal (EPS) adverse event will be defined based on MedDRA PT and determined at blinded data review meeting. The skin-related adverse event will be defined as an adverse event

with any application sites collected on EDC.

- Adverse event (any TEAE)
- Death (TEAE leading to death)
- Serious adverse event (serious TEAE)
- Adverse event leading to treatment discontinuation
 - (TEAE leading to treatment discontinuation)
- Severe adverse event (severe TEAE)
- Extrapyramidal adverse event (extrapyramidal TEAE)
- Skin-related adverse event at the application site (skin related TEAE)

The number and percentage of subjects who have TEAE or treatment-related TEAE will be summarized by SOC/PT for each cohort. If a subject has multiple events categorized in same SOC/PT, the subject will be counted only one time into the SOC/PT. SOCs are sorted by alphabetically and PTs are sorted within SOC in descending order of frequency of cohort total. If there are ties, PTs are sorted by alphabetically. TEAE leading to treatment discontinuation will be summarized in the same manner.

Common TEAE are PT of TEAEs experienced by 2% or more subjects in cohort total. Common TEAE and common treatment-related TEAE will be summarized by SOC/PT.

The number and percentage of subjects who have TEAE or treatment-related TEAE will be summarized by SOC/PT and maximum severity. For this summaries, if a subject experienced more than one episode of a TEAE within a PT, the subject is counted only once in the PT at the maximum severity. If the maximum severity is missing, the episode will be kept as missing (not specified). In determining maximum severity, severities are ranked from missing (not specified), mild, moderate, to severe.

The number and percentage of subjects who have TEAE or treatment-related TEAE will be summarized by SOC/PT and first onset date. If a subject experienced more than one event within a PT, the subject is counted only once in the PT based on the earliest event started on the same or closer to Day 1. Denominator of percentage for each period of interest is the number of subjects who were treated with DSP-5423P in each period.

Onset: Day 1 to 7, Day 8 to 14, Day 15 to 28, Day 29 to 42; Week 1 to 6;
Week 1 to 13; Week 14 to 26; Week 27 to 39; Week 40 or later
(Week 1=Day 1 to 7, Week 2=Day 8 to 14)

As TEAE of interests, Extrapyramidal TEAE and skin related TEAE will be summarized by SOC/PT. Additionally, those TEAE will be summarized by maximum severity or first onset date in same manner as summaries of TEAE. In summary tables, the frequencies for entire TEAE related to extrapyramidal symptoms or TEAE related to skin, not just by SOC/PT, will be presented.

Adverse events and extrapyramidal adverse events started during DSP-5423(tablet) treatment period of Cohort 1, meaning Tab-Day 1 to Day -1 will be summarized by SOC/PT.

Listings for adverse events, AE leading to death, SAE, AE leading to treatment discontinuation, Extrapiramidal AE and skin related AE will be generated. Both TEAE and pre-treatment event which started before Day 1, will be included in those listings. In the listing for skin related AE, the application site will also be presented.

The adverse events during DSP-5423(tablet) treatment period of Cohort 1 will be listed.

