- 16) Laboratory test values, vital signs and body weight

Pharmacokinetic endpoints

- 1) Plasma concentration of bronanserin
- 2) Plasma concentration of bronanserin's metabolites

Other endpoints

- 1) Total score of Drug Attitude Inventory-10(DAI-10)
- 2) EuroQol-5 Dimension (EQ-5D) index values.
- 3) Questionnaire on dosage form

Statistical statistical method:

For efficacy endpoints excluding time to treatment discontinuation from the initial application of DSP-5423P, summary statistics by visit will be provided. Time to treatment discontinuation from the initial application of DSP-5423P will be analyzed using Kaplan-Meier method.

Table 2 Schedule of Assessments (Cohort 1)

			DSP-5423 (tablet) treatment phase (6 weeks)						DSP-5423P treatment phase (52 weeks)												Follow-up phase (1-2 weeks)		
Visit No.	-	1	2	3	4	5	6	101	102	103	104	105	106	107	108	109	110	111	112	113			
Study timeline ^{a)} Week	-	Screening	Timeline from initiation of DSP-5423 (tablet) administration						Timeline from initiation of DSP-5423P application												Discontinuation		
			Tab-Baseline	Tab-Week 1	Tab-Week 2	Tab-Week 4	Tab-Week 6 /baseline	Week 1	Week 2	Week 4	Week 6	Week 8	Week 12	Week 16	Week 20	Week 24	Week 28	Week 36	Week 44	Week 52			
Visit window (Day)	-	Tab-28~	Tab-2~1	Tab-5~11	Tab-12~18	Tab-26~32	Tab-40~43	5~11	12~18	26~32	40~46	54~60	78~92	106~120	134~148	162~176	190~204	239~267	295~323	351~379	At discontinuation +5	6~17 days after completion of treatment or discontinuation	
Obtain informed consent		X																					
Patient demographics and medical history		X																					
Dispense study drug			X ^{d)}	X	X	X	X ^{e)}	X	X	X	X	X	X	X	X	X	X	X	X	X			
Study treatment compliance				X	X	X	X ^{e)}	X	X	X	X	X	X	X	X	X	X	X	X	X	X	X	
PANSS		X	X ^{d)}	X	X	X	X ^{e)}	X	X	X	X	X	X	X	X	X	X	X	X	X	X ^{e)}	X ^{e)}	
CGI-S		X	X ^{d)}	X	X	X	X ^{e)}	X	X	X	X	X	X	X	X	X	X	X	X	X	X	X ^{e)}	
DIEPSS			X ^{d)}	X	X	X	X ^{e)}	X	X	X	X	X	X	X	X	X	X	X	X	X	X ^{e)}	X ^{e)}	
C-SSRS			X ^{d)}	X	X	X	X ^{e)}	X	X	X	X	X	X	X	X	X	X	X	X	X	X ^{e)}	X ^{e)}	
DAI-10							X ^{e)}				X								X		X	X	
EQ-5D							X ^{e)}				X							X		X	X	X	
Skin irritation assessment							X ^{e)}	X	X	X	X	X	X	X	X	X	X	X	X	X	X	X	
Laboratory test ^{b)}		X	X ^{d)}		X		X ^{e)}		X		X		X		X		X	X	X	X	X ^{e)}	X ^{e)}	
Pregnancy test ^{c)}		X																			X	X	
12-lead ECG		X	X ^{d)}		X		X ^{e)}		X		X		X		X		X	X	X	X	X ^{e)}	X ^{e)}	
Body weight		X	X ^{d)}	X	X	X	X ^{e)}	X	X	X	X	X	X	X	X	X	X	X	X	X	X	X	

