10.3 Concomitant medications and therapies

The following information on all medications used from initiation of DSP-5423 administration until the follow-up visit in cohort 1 or initiation of DSP-5423P application until the follow-up visit in cohort 2 will be recorded in the CRFs.:

- Drug name
- Route
- Start date
- Stop date
- The reason for concomitant use
- Drug category
- Daily dose (for antipsychotics and antiparkinson drugs only)

For antipsychotics and antiparkinson drugs, the information on the usage for 7 days before screening and during wash-out period will also be recorded in the CRFs

In this section (Section 10.3), beginning of DSP-5423 (tablet) administration in cohort 1 or beginning of the DSP-5423P application in cohort 2 is defined as "beginning of study drug administration/application".

Table 10 shows restrictions on concomitant medications/therapies.

Table 10 Restrictions on concomitant medications/therapies

	From screening before beginning of study drug administration/application	DSP-5423 (tablet) administration period and DSP-5423P application period	Follow-up period
MAO inhibitors	A	A	C
CYP3A4 inhibitors (External drugs for topical use can be used.)	A	A	A
CYP3A4 inducers (External drugs for topical use can be used.)	A	A	C
Adrenaline	A	A	A
Other investigational products or post-marketed study products	A	A	A
Electroconvulsive therapy	A	A	C
Antipsychotics	B	B	C
Antiparkinson drug	B	B	C
Antimanic and Antiepileptic Drugs	C	B	C
Hypnotic drug	C	B	C
Psychotropic drugs (such as antianxiety drugs and antidepressants)	C	B	C
Treatment drugs for complication	C	B	C

A: prohibited; B: restricted; C: unrestricted

Abbreviations: MAO=monoamine oxidase, CYP3A4=cytochrome P-450 enzyme 3A4

Beginning of study drug administration/application: beginning of DSP-5423 (tablet) administration in cohort 1 or beginning of the DSP-5423P application in cohort 2

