10.3.3 Restrictions on concomitant medications

10.3.3.1 Antipsychotics

Antipsychotics except for the study drug will be restricted as follows:

1) For the subjects not treated with antipsychotics at screening

Antipsychotics will be prohibited from screening until completion of assessments at the last visit (Visit 113) of the DSP-5423P application period or the discontinuation visit.

2) For the subjects treated with any antipsychotics at screening (prior antipsychotics)

The antipsychotics should be tapered and completely discontinued according to procedures a) or b) below, the study drug administration/application will be started. The wash-out period for tapering prior antipsychotics should be up to 4 weeks (28 days) from the screening. Antipsychotics will be prohibited from beginning of study drug administration/application until completion of assessments at the last visit (Visit 113) of the DSP-5423P application period or the discontinuation visit.

a) If the prior antipsychotics dose is 12.0 mg/day or less (haloperidol equivalent)

The prior antipsychotics should be completely discontinued, through tapering during the wash-out period, if needed.

b) If the prior antipsychotics dose is over 12.0 mg/day (haloperidol equivalent)

The prior antipsychotics should be tapered. After the dose of the prior antipsychotics is 12 mg/day or less (haloperidol equivalent), these antipsychotics should be completely discontinued, through tapering during the wash-out period, if needed.

If urgent treatment is required because of psychiatric symptoms such as acute psychomotor excitability, at the discretion of the Investigator, only one antipsychotic drug excluding depot neuroleptics and bilonanserin can be used concomitantly on an as-needed basis. However, all antipsychotics will be prohibited within 48 hours before the PANSS, CGI-S, and C-SSRS assessments. The total duration of concomitant use of antipsychotics for urgent treatment should be 10 days or less through DSP-5423 (tablet) administration period and DSP-5423P application period.

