15.3.6.1 Adverse event

Treatment-emergent adverse event(TEAE) will be summarized. TEAE is defined as the adverse events with start date on or after Day 1. A treatment-related TEAE is defined as a TEAE for which the causal relationship to the study treatment is either 'definite', 'probable', or 'possible'.

The number and percentage of subjects who have TEAE or treatment-related TEAE will be

summarized. Death, Serious TEAE, TEAE leading to treatment discontinuation, severe TEAE, extrapyramidal TEAE, and skin related TEAE will be summarized in the same manner.

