7.2.1 Adverse event

In this study, relevant events occurred from the treatment initiation of DSP-5423 (tablet) to follow-up visit in cohort 1 and ones occurred from the initiation of DSP-5423P application to follow-up visit in cohort 2 will be captured as adverse events. An AE can, therefore, be any unfavorable and unintended sign (including an abnormal laboratory finding), symptom, or disease occurring after the administration of a medicinal (investigational) product, whether or not considered related to the medicinal (investigational) product.

In the cohort 1, AEs that occur during the DSP-5423 (tablet) treatment period and worsen during the DSP-5423P application period will be recorded as both AEs in the DSP-5423 (tablet) administration period and also as AEs in the DSP-5423P application period with start date as the onset date of the worsening AE. AEs that occur during the DSP-5423 (tablet) treatment period without further worsening in the DSP-5423P application period will be recorded as AEs only in the DSP-5423 (tablet) treatment period

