8.5 Analysis Visit

Data of DSP-5423P treatment period is defined as the data captured on Day 1 through 7 days after the final application of DSP-5423P.

All data will be organized and analyzed according to the scheduled timing as outlined in Tables 1 and 2 Schedule of Assessments and according to the visit denoted in the CRFs. Unscheduled visits may not be used for any analysis unless otherwise specified. However, the data collected at the discontinuation visit within 7 days from the final application of study drug are mapped to the next scheduled visit of the actual discontinuation date. In listing, all data including unscheduled visit data should be presented.

1) CRF discontinuation visits in DSP-5423 (tablet) treatment period

Assessments and tests	Relative Day	Analysis Visit
PANSS, CGI-S, DIEPSS, body weight, body temperature, blood pressure, pulse rate	Tab-Day 1 to 11	Tab-W1, 2, 4, 6
	Tab-Day 12 to 18	Tab-W2, 4, 6
	Tab-Day 19 to 32	Tab-W4, 6
	Tab-Day 33 or later	Tab-W6
Laboratory test, ECG	Tab-Day 1 to 18	Tab-W2, 6
	Tab-Day 18 or later	Tab-W 6

The Tab-Day 1 is defined as the date of initial administration of DSP-5423 (tablet). CRF discontinuation visits in DSP-5423 (tablet) treatment period is defined as data on first non-missing (ex. no visit or results are missing) visit which meets all above requirements. Laboratory test and vital sign (body temperature, blood pressure, pulse rate) are performed visit handling for each item. Others are not considered as missing if they have any one component.

2) CRF discontinuation visits in DSP-5423P application period

Assessments and tests	Relative Day	Analysis Visit
PANSS, CGI-S, DIEPSS, C-SSRS,	Day 1 to 11	W1, 2, 4, 6, 8, 12, 16, 20, 24, 28, 36, 44, 52
	Day 12 to 18	W2, 4, 6, 8, 12, 16, 20, 24, 28, 36, 44, 52

Assessments and tests	Relative Day	Analysis Visit
Skin irritation assessment, body weight, body temperature, blood pressure, pulse rate	Day 19 to 32	W4, 6, 8, 12, 16, 20, 24, 28, 36, 44, 52
	Day 33 to 46	W6, 8, 12, 16, 20, 24, 28, 36, 44, 52
	Day 47 to 60	W8, 12, 16, 20, 24, 28, 36, 44, 52
	Day 61 to 92	W12, 16, 20, 24, 28, 36, 44, 52
	Day 93 to 120	W16, 20, 24, 28, 36, 44, 52
	Day 121 to 148	W20, 24, 28, 36, 44, 52
	Day 149 to 176	W24, 28, 36, 44, 52
	Day 177 to 204	W28, 36, 44, 52
	Day 205 to 267	W36, 44, 52
	Day 268 to 323	W44, 52
	Day 324 or later	W52
Laboratory test, ECG	Day 1 to 18	W2, 6, 12, 20, 28, 36, 44, 52
	Day 19 to 46	W6, 12, 20, 28, 36, 44, 52
	Day 47 to 92	W12, 20, 28, 36, 44, 52

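### First-onset TEAE tables count events up to follow-up but divide by subjects treated in the period, so a numerator can include a subject whom its denominator omits; events after a replacement antipsychotic are not distinguished

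*SAP*

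**What the plan says.** **TEAE definition.** SAP 9.12.1: "Treatment-emergent adverse event (TEAE) is defined as adverse events with start date on or after Day 1". Protocol 15.3.6.1 agrees: "TEAE is defined as the adverse events with start date on or after Day 1". Neither sets an end.

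**Collection.** SAP 7.2.1 takes events up to the follow-up visit; for Cohort 2, "ones occurred from the initiation of DSP-5423P application to follow-up visit in cohort 2 will be captured as adverse events". Cohort 1 also ends at follow-up. The schedules of assessments place that visit "6~17 days after completion of treatment or discontinuation".

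**Antipsychotics.** Under Protocol 10.3.3.1 the prohibition ends once the Visit 113 or discontinuation-visit assessments are complete. Table 10 codes the class "Antipsychotics B B C" for pre-treatment, treatment and follow-up, where C means unrestricted.

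**First-onset tables.** SAP 9.12.1 counts each subject once per preferred term, at the earliest onset, and sets the divisor: "Denominator of percentage for each period of interest is the number of subjects who were treated with DSP-5423P in each period". The columns are Days 1–7, 8–14, 15–28 and 29–42, Weeks 1–6, and Weeks 1–13, 14–26, 27–39 and 40 or later. The extrapyramidal and skin-related TEAEs are tabulated by first onset in the same way.

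**The concern.** The numerator runs to the follow-up visit and the denominator stops at the last patch. For a subject who stops shortly before a column ends, a post-patch event falls in the next column, where that subject is not counted as treated. The resulting percentage is not a proportion of the stated group, and it is too high relative to a matched denominator. Only early discontinuers are affected: a completer's follow-up events fall in Week 40 or later, where the completer is already in the denominator.

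The second issue is one of reporting. A subject may leave the patch, start another antipsychotic and then report, say, akathisia. That event counts as a TEAE and, if its preferred term is on the extrapyramidal list, as an extrapyramidal TEAE, with nothing in the tables to show the sequence. SAP 9.7 ends concomitant medication for the patch period at the last application, so a drug started later is absent from those summaries too.

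Safety over 52 weeks is the primary objective and extrapyramidal events are a named endpoint, so these tables will be read closely.

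**Working it through.** **Inputs**
- Tail L: 6 to 17 days (Protocol Tables 2 and 3), taken here as counted from the last patch.
- Column ends: Days 7, 14, 28 and 42; Weeks 13, 26 and 39 end on Days 91, 182 and 273 (7 × 13, 7 × 26, 7 × 39).
- Early stop days: d = 1 to 363.
- Early termination: about half of enrolled subjects (Protocol 15.1).

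**The plan's own figure.** 100 / (1 − 0.5) = 200, which reproduces the enrolment target. So up to about 100 early terminations are expected; some in Cohort 1 may come before any patch.

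**Rule.** With the last patch on day d and a column ending on day b, a mismatch is possible when d ≤ b and d + L ≥ b + 1, that is, b − L + 1 ≤ d ≤ b.

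**Which boundaries count.** Days 7, 14, 28, 91, 182 and 273. Day 42 does not: no short column follows it, and an event on Days 43–59 falls in Weeks 1–13, where the subject is already counted.

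**Stop days at risk**

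| Tail | Short columns | Long columns | Total |
|---|---|---|---|
| 17 days | d = 1–28: 28 | 75–91, 166–182, 257–273: 3 × 17 = 51 | 79/363 = 21.8% |
| 6 days | 2–7, 9–14, 23–28: 3 × 6 = 18 | 86–91, 177–182, 268–273: 3 × 6 = 18 | 36/363 = 9.9% |

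**Examples.** Last patch Day 14, event Day 16: counted in Days 15–28, but the subject was not treated in that period. Last patch Day 91, event on any of Days 92–108 (91 + 17 = 108): counted in Weeks 14–26, again without the subject in the denominator.

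**Weight of the tail.** The off-patch share of a subject's TEAE window is L / (d + L).
- Last patch Day 28: 6/34 = 18% to 17/45 = 38%.
- Last patch Day 364: 6/370 = 1.6% to 17/381 = 4.5%.

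**Would a 7-day cap on TEAEs cure it?** With L = 7 the stop days are 1–7, 8–14 and 22–28 (21) plus 3 × 7 = 21, giving 42/363 = 11.6%. The mismatch shrinks but remains.

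**The case against.** The strongest reply is that TEAE is a label of timing, not of cause. The SAP reports treatment-related TEAEs alongside all TEAEs, and Protocol 12.3 lets the investigator rate an event as not related when another drug plausibly explains it. This stands. A reader might infer that the plan attributes the new drug's effects to the patch; the documents do not support that. The causality rating does not filter the all-TEAE, serious, severe or extrapyramidal counts, but those counts make no causal claim.

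A reader might also see a contradiction with SAP 8.5: "Data of DSP-5423P treatment period is defined as the data captured on Day 1 through 7 days after the final application of DSP-5423P". That section assigns visit assessments to analysis visits, and adverse events are not in its mapping tables. Protocol and SAP agree on the TEAE definition, and the follow-up visit bounds collection in practice. There is no conflict between the two rules.

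A further inference is that TEAEs should stop at 7 days or at the first new antipsychotic. Counting through follow-up is a defensible, conservative choice in a safety study. A cut would move delayed, withdrawal or serious events out of the headline table, and Protocol 10.1.3 protects application sites from light until follow-up, which suggests that late skin reactions are anticipated.

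Finally, measured scales, laboratory values and ECGs at the end of treatment are scheduled before any post-treatment antipsychotic, so the exposed data are mainly reported events over a short tail. All adverse events are listed, so the sequence can be recovered by hand. This limits the size of the problem but does not repair the period percentages.

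**Conclusion.** The denominator mismatch is real and follows directly from the stated rules. It is possible for 10% to 22% of early stop days, depending on whether follow-up falls at 6 or 17 days. Those shares give every stop day from 1 to 363 equal weight and take the tail from the last patch. They show where a miscount could happen, not how often it would. The documents give neither an adverse event rate in follow-up nor a rate of starting replacement drugs, so the distortion itself cannot be sized. It should be negligible for completers and relatively larger for those who stop early.

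The lack of any marker for events after a replacement antipsychotic is a gap in reporting. It does not show that the headline TEAE counts are biased or that their window is wrong.

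**What to change.** In SAP 9.12.1:
1. Define the denominator of every first-onset column as the subjects under adverse event observation in that period, whether on DSP-5423P or in follow-up. Each numerator subject is then in the denominator. Apply this to the all-TEAE, treatment-related, extrapyramidal and skin-related onset tables.
2. Keep the headline TEAE table through follow-up and state that end point explicitly.
3. Add one supplementary table of TEAEs and extrapyramidal TEAEs, split by onset on or before versus after the final application, flagging onset after the first post-treatment antipsychotic. SAP 7.2.2 already records medication start dates to follow-up. Add a line for events whose start date is wholly missing, since SAP 8.7 leaves some undated.

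The TEAE definition does not change, so the SAP stays in line with Protocol 15.3.6.1. The cost is SAP wording, one extra table and slightly larger period denominators. No new data are needed.
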